#### **9.4 Benefit-Risk Assessment**

A risk analysis of the CLAAS device has been performed and concluded that the identified risks have been reduced to a level as low as reasonably practical. When combined with the risk management measures incorporated into the design of the clinical trial, the potential benefits of the clinical use of the CLAAS device in the CONFORMAL Study are judged to justify the potential risks to study participants. The potential benefits and risks of study participation will be evaluated on an individual basis and discussed with each patient prior to enrollment in the study.

### **10.0 Statistical Considerations and Analysis Plan**

#### **10.1 Sample Size Rationale**

The trial will enroll subjects in a staged manner to ensure patient safety in the Early Feasibility Study construct. A total of 20 subjects at 1 center is targeted for this feasibility study.

#### **10.2 Analysis Populations**

##### **10.2.1 Intention to Treat (ITT) Analysis Population**

The Intention to Treat (ITT) analysis population is defined as all subjects enrolled in the study (the point of enrollment is introduction of the CLAAS Access Sheath into the patient's body), regardless of the treatment actually received.

The ITT population will be the primary analysis population for the primary safety endpoint, the primary performance endpoint, and all secondary endpoints and other measures.

##### **10.2.2 The Implanted Patient (IP) Analysis Population**

The Implanted Patient (IP) analysis population is defined as all subjects who leave the catheterization laboratory with an implanted CLAAS device.

The IP population will be the secondary analysis population for the primary safety endpoint, the primary performance endpoint, and all secondary endpoints and other measures.

#### **10.3 Method of Analysis & Reporting**

##### **10.3.1 General Approach**

All endpoints will be reported using appropriate descriptive statistics. Statistics for continuous variables will include sample size, mean, standard deviation, median, interquartile range, minimum, and maximum. Binary variables will be summarized using sample size, frequencies, and percentages. No hypothesis testing will be performed.

Analysis will be conducted using SAS (version 9.3 or greater), unless otherwise noted. Additional details will be pre-specified in the formal Statistical Analysis Plan (SAP) prior to initiation of enrollment.

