## 5.0 Study Design

### 5.1 Study Design Overview

This prospective, single center, open-label, single arm, study will enroll up to 20 subjects aimed at examining the safety and technical performance of the CLAAS device for LAA closure. Patients with non-valvular atrial fibrillation who are at increased risk for stroke and systemic embolism based on CHA2DS2-VASc scores, and who are recommended for oral anticoagulation therapy but have an appropriate rationale to seek a non-pharmacologic alternative to oral anticoagulation, and who meet all eligibility criteria, will be enrolled in the study and undergo LAA closure with the CLAAS system.

Subjects will have clinical follow-up prior to hospital discharge and at 7 days, 45 days, and 6- and 12-months post procedure. Transesophageal echocardiographic (TEE) follow-up will be performed at 45 days and, 6 and 12 months in all subjects.

The primary safety endpoint is freedom from major adverse events, evaluated at hospital discharge or at 7 days post-procedure (whichever occurs later), and defined as absence of the composite of all-cause mortality, ischemic stroke, systemic thromboembolism, and device- or procedure-related adverse events requiring open cardiac surgery or major endovascular intervention. The primary performance endpoint is closure success, defined as device success followed by successful LAA closure (complete closure or peri-device residual leak ≤5 mm in width on TEE at 45 days post-procedure). The study will also report additional secondary safety, performance, and effectiveness endpoints, as well as using TEE to confirm post-procedure ICE evaluation of device seal and position as a comparator for device success.

All endpoints will be reported using appropriate descriptive statistics in the primary analysis population (the ITT population), and no hypothesis testing will be performed. As a secondary analysis, all endpoints will be evaluated in the Implanted Patient (IP) population.

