### 5.3.3 Secondary Endpoints

Unless otherwise indicated, the following secondary endpoints will be evaluated in-hospital and at 45 days, and 6 and 12 months.

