#### 5.3.3.1 Secondary Safety Endpoints

5.3.3.1.1 **Major procedure-related complications**, defined as the composite of cardiac perforation, pericardial effusion with tamponade, ischemic stroke, device embolization, and major vascular complications as related to the study device or procedure [evaluated in-hospital]

5.3.3.1.2 **Major safety events**, defined as the composite of all-cause mortality, overt CNS injury (Neuro ARC defined), and major bleeding (BARC Type 3-5)

5.3.3.1.3 **Mortality**, classified as cardiovascular or non-cardiovascular reported cumulatively and individually

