## **6.6 Withdrawal, Loss to Follow-up, and Study Completion**

### **6.6.1 Voluntary Withdrawal**

Subjects can withdraw from the study at any time; the reason(s) for withdrawal (if given) will be documented. All data available at the time of withdrawal (if any) will be used for analysis, unless the subject has explicitly forbidden the use of such data and has documented this preference in accordance with local regulatory requirements. There will be no further follow-up (per this study protocol) on a subject who has withdrawn. Subjects who withdraw from the study will not be replaced. The withdrawal of a subject can be initiated by the Investigator if he/she determines it is in the best interest of the patient.

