# **10.0 Statistical Considerations and Analysis Plan**

## **10.1 Sample Size Rationale**

The trial will enroll subjects in a staged manner to ensure patient safety in the Early Feasibility Study construct. A total of 20 subjects at 1 center is targeted for this feasibility study.

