## **10.2 Analysis Populations**

### **10.2.1 Intention to Treat (ITT) Analysis Population**

The Intention to Treat (ITT) analysis population is defined as all subjects enrolled in the study (the point of enrollment is introduction of the CLAAS Access Sheath into the patient's body), regardless of the treatment actually received.

The ITT population will be the primary analysis population for the primary safety endpoint, the primary performance endpoint, and all secondary endpoints and other measures.

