## **10.3 Method of Analysis & Reporting**

### **10.3.1 General Approach**

All endpoints will be reported using appropriate descriptive statistics. Statistics for continuous variables will include sample size, mean, standard deviation, median, interquartile range, minimum, and maximum. Binary variables will be summarized using sample size, frequencies, and percentages. No hypothesis testing will be performed.

Analysis will be conducted using SAS (version 9.3 or greater), unless otherwise noted. Additional details will be pre-specified in the formal Statistical Analysis Plan (SAP) prior to initiation of enrollment.

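### Crude percentages for mortality, major safety events and embolic events at 6 and 12 months will be biased if any ITT subject leaves early, so state the denominator and add time-to-event estimates beside them

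*Combined protocol and SAP*

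**What the plan says.** The relevant text is the same in Versions A and B.

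- **Method.** Section 10.3.1: "Binary variables will be summarized using sample size, frequencies, and percentages". It adds that "No hypothesis testing will be performed" and leaves further detail to a formal SAP that is not among these documents. Section 10.3.3 makes no adjustment for missing data beyond summarising loss to follow-up.
- **Time points.** Section 5.3.3: unless otherwise indicated, "the following secondary endpoints will be evaluated in-hospital and at 45 days, and 6 and 12 months". This covers major safety events, embolic events and mortality, the last "classified as cardiovascular or non-cardiovascular reported cumulatively and individually" (section 5.3.3.1).
- **Population.** Section 10.2.1: "The ITT population will be the primary analysis population". It includes subjects in whom the sheath was introduced but no device was left in place.
- **Early exit.** Section 6.6.1: "There will be no further follow-up (per this study protocol) on a subject who has withdrawn". Withdrawn subjects are not replaced. Loss to follow-up needs three consecutive missed visits (section 6.6.2).
- **Later visits.** Sections 7.8 and 7.9 write the 6- and 12-month visits for subjects who received an implant, and section 6.6.3 defines a final assessment only for them. Section 5.1 and Table 3 carry no such limit.
- **Size.** Section 10.1: "A total of 20 subjects at 1 center is targeted for this feasibility study". No dropout, implant-failure or event rate is stated.

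**The concern.** These endpoints are cumulative risks, and a simple percentage is a sound estimate of a cumulative risk only when every subject's status at the time point is known. A subject last seen free of events on day 60 counts as event-free for a full year when the divisor is all enrolled. Dividing by completers keeps every event but discards the event-free time of those who left.

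The planned summary of loss to follow-up may not reveal the problem. After the 45-day visit only two visits remain, so a subject who attends at day 45 and never returns cannot reach three consecutive missed visits.

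The study is meant to supply preliminary safety and effectiveness data for the design of a pivotal trial (section 4.3), and these are its 12-month clinical event rates. Without a rule, the divisor can be chosen after the results are known.

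**Working it through.** The plan has no figure of its own to reproduce: the target of 20 comes with no rate, precision or power input. The check therefore compares three estimators of 12-month risk.

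**1. Worked case.** Assume 20 subjects, events on days 20, 200 and 300, two subjects leaving at day 45 and three at day 120.

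- All enrolled: 3/20 = 15.0%.
- Completers (event or full follow-up): 3/(20 − 5) = 3/15 = 20.0%.
- Kaplan-Meier: the numbers at risk are 20 at day 20, 20 − 1 − 5 = 14 at day 200, and 13 at day 300. The estimate is 1 − (19/20)(13/14)(12/13) = 18.6%.

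**2. Average bias.** This is a simulation. From the documents: n = 20, and a 12-month visit at ±30 days (about days 335 to 395). Assumed: true 12-month risk 15%, constant event and withdrawal hazards, visits uniform over the window, non-implanted subjects last seen at day 45, and exits unrelated to risk. Mean estimates:

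| Withdrawal per year | Not implanted | All enrolled | Completers | Kaplan-Meier, day 365 |
|---|---|---|---|---|
| 20% | 10% | 12.3% | 16.7% | 14.9% |
| 10% | 5% | 13.6% | 15.8% | 15.0% |
| 0% | 10% | 13.6% | 15.1% | 14.9% |
| 0% | 0% | 15.0% | 15.0% | 15.0% |

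In the first two rows, dividing by all enrolled falls short by 15 − 12.3 = 2.7 and 15 − 13.6 = 1.4 points. Dividing by completers overshoots by 16.7 − 15 = 1.7 and 15.8 − 15 = 0.8 points. The third row shows that bias can arise without any withdrawal if non-implanted subjects are not followed.

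**3. Sampling error.** The exact 95% interval is 3.2-37.9% for 3/20 and 1.2-31.7% for 2/20. Root-mean-square error in the first scenario is 7.8 points for all enrolled and 9.1 for Kaplan-Meier at day 365. In the second it is 7.8 and 8.6.

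**4. Numbers at risk.** With censoring at the last visit, half the visits fall before day 365. The expected number still at risk is about:

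- Day 365: 20 × 0.90 × 0.80 × 0.85 × 0.5 = 6.1 (first scenario); 20 × 0.95 × 0.90 × 0.85 × 0.5 = 7.3 (second).
- Day 335: 20 × 0.90 × (0.80 × 0.85)^(335/365) = 12.6; 20 × 0.95 × (0.90 × 0.85)^(335/365) = 14.9.

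A day-335 estimate refers to a slightly shorter period: 1 − 0.85^(335/365) = 13.9% when the 365-day risk is 15%.

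**5. Informative exit.** Take a 10% risk while in the study and three times the hazard after leaving. The true rate is then 10.9% with 10% dropout and 11.8% with 20%. Kaplan-Meier still averages 10.0% and 9.9%.

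**The case against.** The strongest case against acting is that the crude percentage is good enough here. The study is single-arm and descriptive, with no test and no rule tied to a 12-month rate, and both primary endpoints fall by 45 days or, for safety, at discharge or day 7. A shift of 1-3 points is lost in intervals more than 30 points wide, and in both scenarios with withdrawal the crude rate had the smaller root-mean-square error. Sample sizes accompany the percentages and endpoint listings are planned, so a reader could follow individual cases. All of this stands. It argues for adding estimates beside the planned percentages, not replacing them.

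Four stronger readings are tempting, and the documents do not support them.

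- **That the 12-month rate is biased whichever denominator is used.** The bias exists only if someone leaves early, and no exit rate is given.
- **That Kaplan-Meier would cure it.** It assumes that those who leave have the same risk as those who stay. That is doubtful after a failed implantation, and no estimator supplies missing follow-up.
- **That non-implanted subjects certainly have no follow-up after day 45.** Sections 7.8 and 7.9 point that way. Section 5.1 and Table 3 do not, and section 8.8.1 collects adverse events from enrollment to study closure without limiting this to implanted subjects.
- **That the plan excludes time-to-event methods.** It refers to appropriate descriptive statistics and defers detail to a SAP not available here. That leaves room for the remedy but does not show that it exists.

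**Conclusion.** The point holds in conditional form. If any ITT subject leaves, or has no scheduled contact, before 12 months, the crude 12-month percentages are biased. The size is about 1-3 points downward over all enrolled and 1-2 points upward over completers, under an assumed 15% risk, 10-20% withdrawal, 5-10% not implanted and exits unrelated to risk. The same mechanism applies at 6 months; its size there was not calculated. With complete follow-up the bias is zero.

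This is a modest gap in pre-specification, small beside sampling error, and it does not touch the primary endpoints. It merits a change because the same data could be reported as 15% or 20%, as the worked case shows, and fixing the rule beforehand is cheap.

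**What to change.** In sections 10.3.1 and 10.3.3 (or the formal SAP):

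1. Keep the planned counts, percentages and listings. State the denominator and the number with known status at 45 days, 6 months and 12 months.
2. Add, in ITT, Kaplan-Meier estimates for mortality and for major safety events (a composite that includes death). For embolic events use cumulative incidence with death as a competing event. For cardiovascular and non-cardiovascular death use cumulative incidence with the other cause competing. Give numbers at risk and 95% intervals, and censor at last contact.
3. Report the 12-month estimate at a day in the visit window when enough subjects remain at risk, for example day 335, and label it with that day.
4. Confirm that event dates and last-contact dates are recorded. The adverse event and completion forms imply them, but the protocol does not name them as fields.
5. Reconcile section 5.1 and Table 3 with sections 6.6.3, 7.8 and 7.9 on follow-up of non-implanted ITT subjects.

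Items 1 to 3 cost a few lines of text and code. Item 5 may add contacts, depending on how the sections are reconciled. The added estimates have larger variance than the crude percentage and will usually be slightly higher than the rate over all enrolled.

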### 10.3.2 Baseline Characteristics

The following data will be summarized using descriptive statistics and presented for the ITT and IP populations:

- Baseline demographics
- Baseline comorbidities, risk factors, and medical history
- Cardiac risk factors and cardiac history
- Procedural characteristics
- Device details

### 10.3.3 Endpoint Analysis

All endpoints will be reported in the ITT population using appropriate descriptive statistics. No formal hypothesis testing will be performed. As an additional analysis, all endpoints will be evaluated in the IP population.

All efforts will be made to minimize the amount of missing data; where it occurs, the reasons and counts and percentages of subjects with loss to follow-up will be summarized. In the final analyses, no adjustment will be made for missing data.

### 10.3.4 Additional Analyses

The following data will be summarized using descriptive statistics presented by treatment group in the ITT and IP populations:

- Frequency (number and percentage of patients) with each type of concomitant medication
- Frequency (number and percentage of patients) with each site-reported Treatment Emergent AE overall and by MedDRA system organ class and preferred term (a treatment emergent AE is an AE that started or worsened during or after the index procedure)
- Frequency (number and percent of patients) with each site-reported Treatment Emergent Serious AE overall and by MedDRA system organ class and preferred term
- Protocol deviations (number and percentage of patients with each deviation type)
- Detailed listings on primary and secondary endpoints, site-reported AEs, and protocol deviations

## 11.0 Publication Policy

The data obtained from this study may be presented for publication and/or presentation as long as Conformal and all investigators and authors assure that no information, which would reveal a subject's identity, is used in any publication. Information, which could be used to establish a subject's identity, should not be provided to Conformal. Authors and Conformal will take every reasonable precaution to protect the identity of subjects enrolled in the study.

## 12.0 Data Collection and Monitoring

### 12.1 Data Collection and Monitoring

All required data for this study will be collected on standardized Case Report Forms (CRFs). The investigator (or designated hospital staff) will assure primary data collection based on source-documented hospital chart reviews.

Monitoring will be performed by the Sponsor and/or its designee(s) to ensure that the investigator and his/her study team conduct the clinical investigation in accordance with contract specifications, this protocol, the Declaration of Helsinki, ICH-GCP, ISO 14155, 21 CFR Part 812, and other applicable FDA and local regulations, and to ensure adequate protection of the rights and safety of subjects and the quality and integrity of the resulting data. All monitors will receive study-specific training on the Clinical Investigation Plan, the CRF, and the use of the investigational device in accordance with Sponsor SOPs.

Submitted trial data will be verified against patient charts and other sources containing original records of patient data. Source document verification will occur in accordance with the pre-specified Monitoring Plan. The Investigator/institution will permit direct access to source data/documents in order for trial-related monitoring, audits, EC review and regulatory inspections to be performed.

Progress of the trial will be monitored by:

- On-site review, as deemed appropriate by the Sponsor
- Telephone communications between site personnel (e.g., Site Investigator, Trial Coordinator) and trial monitors
- Review of CRFs and associated clinical records
- Review of regulatory documents

If a monitor becomes aware that an Investigator is not complying with the requirements mentioned above, the sponsor will be notified by the monitor. The Sponsor will evaluate the non-compliance and if necessary, immediately either secure compliance or discontinue shipments of the investigational device to the Investigator and terminate the Investigator's participation in continued enrollment in the investigation. The Investigator will be required to return all unused devices to the Sponsor.

### 12.2 Source Documentation

Auditors, monitors, ECs, the Sponsor, and the FDA and other regulatory authorities may have access to the medical records related to this study. Original or certified copies of all relevant clinical findings, observations, and other activities throughout the clinical investigation must be recorded and maintained in the medical file of each enrolled patient (no source documentation will be recorded directly on the CRF). At a minimum, the following must be included in each patient's file:

- Sufficient medical history and current physical condition, including any medication(s) the patient is taking at the time of the procedure to assess the patient's eligibility;
- The medical file should reveal the patient's participation in this study, including documentation of written informed consent;

- Dated report of the index procedure including medication, material usage, and complications, if applicable;
- Dated reports of the post-procedure / pre-discharge and follow-up assessments;
- Dated results of required laboratory tests;
- Any adverse event(s), the resultant action or treatment, and outcome, if applicable; and
- In the case of withdrawal of patient consent, the reason and patient status at time of withdrawal.

The Site Investigator will permit study-related monitoring, audits, EC review, and FDA and other applicable regulatory authority inspections by allowing direct access to the source data.

In case of electronic source data, periodic access will be allowed for full safety review. The review will be specific to study subjects and the records that would contain potential safety data. Dated print-outs are acceptable for preliminary review of safety information. Print-outs will not be limited to cardiac data only but should include all available data related to the identified patient(s).

### **12.3 Auditing**

As a quality assurance measure, investigational sites may be audited during the trial or following trial completion. The purpose of an audit is to provide an independent evaluation of trial conduct and protocol and GCP compliance, separate from routine monitoring and quality control functions. The audit may be conducted by Conformal Medical personnel (or designee), the FDA, or another regulatory body.

Site Investigators are requested to notify the Sponsor if the FDA or other regulatory body requests an audit. The site investigator and/or institution shall permit Conformal Medical (or designee) personnel and regulatory body representatives direct access to source data and all other relevant documents.

## **13.0 Device Accountability**

Information regarding opened, introduced, and implanted CLAAS devices will be recorded on the applicable CRF. Information regarding opened and introduced delivery systems will also be recorded on the applicable CRF.

Investigational devices will be shipped after documentation of site activation is sent to the site and shipping authorization is completed.

The principal investigator or an authorized designee must maintain a device accountability log documenting the date of receipt, the identification of each investigational device (i.e. serial number), the subject identification, the date of use, and final disposition. Devices must be stored in a locked location with access restricted only to investigators and authorized research personnel

